19.3 MODIFIED ACTIVITY-BASED COSTING METHODOLOGY

Introduction

Modified activity-based costing methodology will be used in this study to document direct costs (direct reimbursable medical cost, direct non-reimbursable medical costs, direct non-medical costs) and indirect costs related to each treatment group. Modified activity-based costing (ABC) is an accounting technique that allows healthcare organizations to determine actual costs associated with their services based on the resources they consume.

Direct medical costs related to care of venous leg ulcers include 1) labor for office visits, diagnostics, laboratory tests, debridement, application of treatment to the wound, applying compression bandages etc. This may be accomplished through a physician, nurse or other qualified healthcare professional; 2) materials such as wound dressings, compression bandages and medical supplies (gloves, saline, gauze etc.); 3) medications for pain, infection etc. and 4) the treatment under investigation. Indirect costs will be estimated by results from the Patient Benefit Index questionnaire (Appendix 19.6).

Sampling Institutions for Direct Human Clinical Resource, Medical Supplies and Diagnostics Costing Analysis

Wound clinics participating in the study will be randomly selected and given 5 costing worksheets (5 patients) for CelluTome™ group (see figures on next 3 pages) and 5 costing worksheets (5 patients) for the control group in each institution to document the weekly direct human clinical resource time for each group. This involves clinical contact within the wound clinic and during the week with non-wound clinic staff (e.g., primary care physicians, home care nurse, RN etc.). An assigned clinician or research assistant will collect the information contained within the costing worksheet for each patient randomly selected within each wound clinic. This data will be used to estimate direct human clinical resource consumption and average costs for each group.

	CelluTome Group	Research Clinic: _____ Visit Date: _____	Activity-Based Costing Worksheet Clinic Labor Patient Id: _____												

Pre-CelluTome Application: Includes compression bandage removal, dressing(s) removal, ulcer cleansing, patient assessment etc.
 
Please place a check () in boxes indicating staff credentials administering care to this patient. Enter number of staff for each credential and then total minutes allotted for all respective clinicians:
 
 
  RN	Number of Registered Nurses: _____	Total Minutes for all RN's at this pre-CelluTome application phase: _____	
 
  LPN	Number of Licensed Practical Nurses: _____	Total Minutes for all LPN's at this pre-CelluTome application phase: _____	
 
  Nurse Other*	Number of Other Nurses: _____	Total Minutes for all other nursing at this pre-CelluTome application phase: _____	
 
  Physician	Number of Physicians: _____	Total Minutes for all Physician's at this pre-CelluTome application phase: _____	
 
 
*Please describe nurse other in CelluTome application phase: _____
				 RN	Number of Registered Nurses: _____	Total Minutes for all RN's at this pre-CelluTome application phase: _____	 LPN	Number of Licensed Practical Nurses: _____	Total Minutes for all LPN's at this pre-CelluTome application phase: _____	 Nurse Other*	Number of Other Nurses: _____	Total Minutes for all other nursing at this pre-CelluTome application phase: _____	 Physician	Number of Physicians: _____	Total Minutes for all Physician's at this pre-CelluTome application phase: _____
 RN	Number of Registered Nurses: _____	Total Minutes for all RN's at this pre-CelluTome application phase: _____													
 LPN	Number of Licensed Practical Nurses: _____	Total Minutes for all LPN's at this pre-CelluTome application phase: _____													
 Nurse Other*	Number of Other Nurses: _____	Total Minutes for all other nursing at this pre-CelluTome application phase: _____													
 Physician	Number of Physicians: _____	Total Minutes for all Physician's at this pre-CelluTome application phase: _____													

CelluTome Application: Includes 1) site preparation; 2) position harvester; 3) blister formation; 4) graft acquisition & application to recipient site; 5) donor site care
 
Please place a check () in boxes indicating staff credentials administering CelluTome to this patient. Enter number of staff for each credential and then total minutes allotted for all respective clinicians:
 
 
  RN	Number of Registered Nurses: _____	Total Minutes for all RN's at this CelluTome application phase: _____	
 
  LPN	Number of Licensed Practical Nurses: _____	Total Minutes for all LPN's at this CelluTome application phase: _____	
 
  Nurse Other**	Number of Other Nurses: _____	Total Minutes for all other nursing at this CelluTome application phase: _____	
 
  Physician	Number of Physicians: _____	Total Minutes for all Physician's at this CelluTome application phase: _____	
 
 
**Please describe nurse other in pre-CelluTome phase: _____
				 RN	Number of Registered Nurses: _____	Total Minutes for all RN's at this CelluTome application phase: _____	 LPN	Number of Licensed Practical Nurses: _____	Total Minutes for all LPN's at this CelluTome application phase: _____	 Nurse Other**	Number of Other Nurses: _____	Total Minutes for all other nursing at this CelluTome application phase: _____	 Physician	Number of Physicians: _____	Total Minutes for all Physician's at this CelluTome application phase: _____
 RN	Number of Registered Nurses: _____	Total Minutes for all RN's at this CelluTome application phase: _____													
 LPN	Number of Licensed Practical Nurses: _____	Total Minutes for all LPN's at this CelluTome application phase: _____													
 Nurse Other**	Number of Other Nurses: _____	Total Minutes for all other nursing at this CelluTome application phase: _____													
 Physician	Number of Physicians: _____	Total Minutes for all Physician's at this CelluTome application phase: _____													

CelluTome	Clinic Labor (continued)

Post CelluTome Application: Includes compression bandage application and other activity before patient leaves the research clinic
 
Please place a check () in boxes indicating staff credentials administering compression bandage to this patient and other care before patient leaves clinic. Enter number of staff for each credential and then total minutes allotted for all respective clinicians:
	
 RN	Number of Registered Nurses: _____ Total Minutes for all RN's at this post-CelluTome application phase: _____
 LPN	Number of Licensed Practical Nurses: _____ Total Minutes for all LPN's at this post-CelluTome application phase: _____
 Nurse Other***	Number of Other Nurses: _____ Total Minutes for all other nursing at this post-CelluTome application phase: _____
 Physician	Number of Physicians: _____ Total Minutes for all Physician's at this post-CelluTome application phase: _____
***Please describe nurse other in post-CelluTome phase: _____	

Non-Clinic Care in Addition to Clinic Care
 
How many nursing visits to patients home has patient received in the last 7 days to treat their ulcer?  None  1  2  3  > 3
 
If not under home care have they visited their primary care physician for ulcer care in last 7 days?  No  Yes - how often?  1  2  3  > 3
 
If not under home care or physician care has the patient receive wound care in a skilled nursing or long term care facility last 7 days?  Yes  No
 
Other non-clinic care? (please explain) _____
	

Notes:
 <hr/> <hr/> <hr/>	

Patient Id: _____ Visit Date: _____

CelluTome Study ABC Worksheet, Confidential KCI 2015

Page 2 of 2

 
Standard Care Group
	
Research Clinic: _____
 
Visit Date: _____ Patient Id: _____
	
Activity-Based Costing Worksheet
 
Clinic Labor
												

Entire Clinic Visit: Includes compression bandage removal, dressing(s) removal, ulcer cleansing, patient assessment, dressing application and compression bandaging etc.
 
Please place a check () in boxes indicating staff credentials administering care to this patient. Enter number of staff for each credential and then total minutes allotted for all respective clinicians:
 
 
  RN	Number of Registered Nurses: _____	Total minutes for all RN's at this clinic visit: _____	
 
  LPN	Number of Licensed Practical Nurses: _____	Total minutes for all LPN's at this clinic visit: _____	
 
  Nurse Other*	Number of Other Nurses: _____	Total minutes for all other nursing at this clinic visit: _____	
 
  Physician	Number of Physicians: _____	Total minutes for all Physician's at this clinic visit: _____	
 
			 RN	Number of Registered Nurses: _____	Total minutes for all RN's at this clinic visit: _____	 LPN	Number of Licensed Practical Nurses: _____	Total minutes for all LPN's at this clinic visit: _____	 Nurse Other*	Number of Other Nurses: _____	Total minutes for all other nursing at this clinic visit: _____	 Physician	Number of Physicians: _____	Total minutes for all Physician's at this clinic visit: _____
 RN	Number of Registered Nurses: _____	Total minutes for all RN's at this clinic visit: _____												
 LPN	Number of Licensed Practical Nurses: _____	Total minutes for all LPN's at this clinic visit: _____												
 Nurse Other*	Number of Other Nurses: _____	Total minutes for all other nursing at this clinic visit: _____												
 Physician	Number of Physicians: _____	Total minutes for all Physician's at this clinic visit: _____												

*Please describe nurse other in the visit: _____
														

Non-Clinic Care in Addition to Clinic Care
 
How many nursing visits to patients home has patient received in the last 7 days to treat their ulcer?  None  1  2  3  > 3
 
If not under home care have they visited their primary care physician for ulcer care in last 7 days?  No  Yes - how often?  1  2  3  > 3
 
If not under home care or physician care has the patient receive wound care in a skilled nursing or long term care facility last 7 days?  Yes  No
 
Other non-clinic care? (please explain) _____
														

Notes:
 
_____
 
_____
 
_____
														

Patient Consumption of Drugs, Skin Care, Medical Supplies and CelluTome™

The patients randomly selected at the eight wound clinics will have their consumption of medical supplies (e.g., dressings, compression bandages, debridement, tape, gloves, saline and, gauze etc.), drugs (e.g., antibiotics, pain meds, antimicrobials etc.) and CelluTome™ documented in the patient record (CRF) over the course of their assigned therapy. A research assistant or assigned nurse will pull the records for each patient and document the consumption and costs of medical supplies and CelluTome™ for health economic analysis.

Laboratory and Miscellaneous Diagnostics

A record of diagnostics used within the treatment process is contained in the randomly assigned patient medical record and case report form. A research assistant or assigned nurse will pull the records for each patient and document the consumption and costs of diagnostics for health economic analysis.

Cost Analysis

Multiple costing perspectives are considered in the health economic analysis:

Hospital/Outpatient Perspective: Direct institutional medical costs for the treatment and control group will be collected through modified activity-based costing methodology. Hourly payment rates will be collected directly from the institutions where care is provided for each care provider involved in the treatment for each cohort. An average hourly payment rate per resource will be determined across the

institutions participating in the study. For resource consumption outside of the wound clinic national hourly wage rates will be determined for home care visits, nursing home staff, family caregiver etc. as detected in modified activity-based costing data collection forms. All direct medical costs from the hospital/outpatient sector will be compiled for each cohort and compared between groups as the patients flow through the study/system. This allows a pragmatic view of costs and cost savings from the hospital/outpatient perspective in relation to their charges and reimbursement.

Payer Perspective: Reimbursement from Medicare, Medicaid and Private payers during the course of the study for each group are compiled from each institution participating in the study. Average reimbursement for each product/procedure/stay for each cohort and patient will be determined across the institutions. This information will come from data sources within each institution as compiled by an internal research assistant. Cost effectiveness analysis from the payer perspective is expected to show reduced reimbursement costs for CelluTome group in respect to expedited healing and reduction in complications.

[figure not shown]
Patient Perspective: Patient costs will be determined from the patient or proxy related to the direct care (medicine, hospital, therapy etc.) that are out-of-pocket, indirect work loss, worker replacement, and reduced productivity from the ulcer.

A comparative cost-benefit, cost-utility and cost-effectiveness analysis will be derived from a discrete-event simulation model with a time-frame conducive to each perspective above (Appendix 19.4). For the hospital/outpatient clinic a return-on-investment (cost-benefit) is determined over 6 to 12 treatment weeks which is standard length-of-time patient is engaged with that sector. From a payer perspective, the model will highlight costs from 1 to 3 years as VLU patients that do not heal within 6 months continue with treatment expenses. Fortunately, patients that do not heal within 6 months are few (~10 percent) but still costly. Reduction in patient out-of-pocket expenses will be compared over the entire span of the model (3 years).

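### Both costing worksheets lack a structured field for a second or third source of outside care and lack full counts, so outside-clinic cost may be understated by an unknown amount

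*Combined protocol and SAP*

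**What the plan says.** Section 19.3 of the protocol (Modified Activity-Based Costing Methodology) sets up worksheets for a sample of patients in each arm. Besides clinic labour, they are to cover contact "during the week with non-wound clinic staff (e.g., primary care physicians, home care nurse, RN etc"; the kinds of staff are listed together, not as alternatives.

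The block on care outside the clinic has the same wording on the CelluTome and the Standard Care worksheet:

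1. Home nursing, asked of everyone: "How many nursing visits to patients home has patient received in the last 7 days to treat their ulcer". The answers are none, 1, 2, 3 or more than 3.
2. Physician visits, asked conditionally: "If not under home care have they visited their primary care physician for ulcer care in last 7 days". The answer is no, or yes with 1, 2, 3 or more than 3.
3. Facility care, with a double condition: "If not under home care or physician care has the patient receive wound care in a skilled nursing or long term care facility". The answer is yes or no.
4. An unconditional open item: "Other non-clinic care? (please explain". A notes field follows.

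For the hospital/outpatient perspective, the cost analysis in Section 19.3 applies national hourly wage rates to care outside the wound clinic, including home visits and nursing home staff, "as detected in modified activity-based costing data collection forms". For the payer perspective, reimbursement data "are compiled from each institution participating in the study". Patient costs come from the patient or a proxy.

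**The concern.** The conditions on items 2 and 3 treat the three sources as mutually exclusive within a week. Completed as worded, the form gives a patient under home care nowhere structured to enter a physician visit or facility care, and gives a patient under physician care nowhere structured to enter facility care. Separately, the facility tick box and the open top category give no quantity for an hourly rate to multiply.

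Cost-effectiveness and cost-benefit are listed secondary objectives and outcomes (Sections 1 and 3), and the simulation model in Section 19.4 takes clinical human resources as a cost input. The sample is small: 5 patients per arm per clinic and, with the eight clinics mentioned in Section 19.3, 5 × 8 = 40 per arm. One patient is then 1/40 = 2.5% of an arm's sample, so a few incompletely recorded patients can move the average.

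**Working it through.** The plan states no figure on this point, so there is none to reproduce. The check is a reading of the form against its purpose, followed by illustrations on labelled assumptions.

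**Form against purpose**

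| Care in the week | Structured items as worded | Left for free text |
|---|---|---|
| Home nursing and physician | Home visits | Physician visits |
| Home nursing and facility | Home visits | Facility care |
| Physician and facility | Physician visits | Facility care |
| All three | Home visits | Physician visits and facility care |
| Facility only | Yes, no quantity | Number of contacts |
| More than 3 visits of one kind | Above 3, no quantity | Actual number |

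The first source in the sequence is always recorded. Section 19.3 has no rule for costing a skipped item, a free-text entry or the top category. Section 9.7 carries the last observation forward for missing secondary endpoints, but does not say whether an item skipped by design counts as missing. A patient under home care every week would have no earlier physician entry to carry forward.

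**Overlap, on assumptions**

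Let h, p and f be the weekly shares of patients with home, physician and facility care. Assume that the three are independent, that each means one contact, and that nothing is written as free text.

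- Contacts: h + p + f.
- Missed: h·p + f·[1 − (1 − h)(1 − p)].
- Low case, h = 0.10, p = 0.10, f = 0: missed 0.01 of 0.20, or 5%.
- High case, h = 0.50, p = 0.30, f = 0.10: missed 0.15 + 0.10 × (1 − 0.50 × 0.70) = 0.15 + 0.065 = 0.215 of 0.90, or 23.9%.

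For one patient with a home visits and b physician visits in the same week, the missed share is b/(a + b). With a and b each from 1 to 3 it runs from 1/4 = 25% to 3/4 = 75%.

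The overlap loss is 0 if no patient has overlapping care, or if the free-text item is used and costed.

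**Top category, on assumptions**

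If more than 3 were costed as 4, n true visits would lose 1 − 4/n: 0 at n = 4, 20% at n = 5 and 43% at n = 7. The plan gives neither the scoring value nor the distribution of n.

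**Difference between arms**

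Let C be true outside-clinic cost and L the part not captured, with subscripts S for standard care and T for CelluTome. The recorded difference is (C_S − C_T) − (L_S − L_T). It is unchanged if L_S = L_T, smaller than the true difference if L_S − L_T has the same sign as C_S − C_T (and no larger in size), and exaggerated if the signs are opposite. The documents give no value for either L.

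**The case against.** The strongest reply is that the form already has a safety net. The open item and the notes field are unconditional, so a physician visit by a home-care patient can be written there. This stands as far as it goes: the care is not necessarily lost. However, an item headed as other care, placed after three items that name home nursing, physicians and facilities, is likely to be read as care of a different kind. Nothing tells staff to enter a skipped visit there, and nothing says how the text becomes a cost.

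A second reply is that outside care may be rare, because the protocol directs ulcer care to the site: compression is applied at every visit (Section 7.3), patients call or visit the site about a soiled or removed bandage (Section 7.4), and unscheduled site visits are provided for (Section 6.3). This also stands. It bears on the size of the problem, which the documents leave open.

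A reader might go further in three ways, none supported by the documents:

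- That care from more than one source is scored as zero. The first source is recorded, and no section scores a skipped item as zero.
- That a definite share is lost, such as 20–50% of physician visits or 43% of home-nursing cost. The first restates an assumed overlap rate. The second needs seven visits in the week and a value of 4 for the top category, and the plan gives neither.
- That the cost difference between arms necessarily shrinks. The wording is identical in both arms, and no overlap rates by arm are given.

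The reach is also limited. Section 19.4 ties cost-effectiveness to the payer, and payer and patient costs have their own sources. The worksheet route is described under the hospital/outpatient perspective.

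**Conclusion.** The point holds as a minor weakness in form design for secondary economic outcomes. On both worksheets the conditional wording leaves no structured field for overlapping outside care, facility care has no count, and visits above 3 are not counted. That is at odds with the stated aim of Section 19.3 and with its hourly-rate costing of care detected on the forms.

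Outside-clinic cost, mainly in the hospital/outpatient perspective, may be understated. The amount is unknown. The 5% to 24% range concerns contacts, not cost, and rests on assumed usage, independence, one contact per source and unused free text. The facility tick and the top category leave a gap even without overlap, whose size depends on a scoring rule that the plan does not state. The direction and size of any effect on the difference between arms are not established.

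**What to change.** On both worksheets:

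1. Delete the conditional openings of the physician and facility items, so that every patient is asked every item.
2. Record the number of home nursing and physician visits in place of the categories ending above 3.
3. Replace the facility yes/no with the number of wound-care contacts in the last 7 days.
4. State in Section 19.3 how blanks and free-text entries are costed.

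The cost is a change of form wording, one added costing rule and slightly longer completion of each worksheet. No clinical procedure is affected.

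### Care outside the clinic is costed only under the hospital perspective, so the payer result omits reimbursed outside care, and the hourly-wage rule does not fit the worksheets

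*Combined protocol and SAP*

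**What the plan says.** Cost-effectiveness and cost-benefit are secondary outcomes (Synopsis; section 3). Appendix 19.3 defines three costing perspectives, and 19.4 runs them through a simulation model.

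- **Hospital/outpatient (19.3).** The paragraph opens with institutional cost: "Direct institutional medical costs for the treatment and control group will be collected through modified activity-based costing methodology". It then covers care elsewhere: "For resource consumption outside of the wound clinic national hourly wage rates will be determined for home care visits, nursing home staff, family caregiver". It closes with: "All direct medical costs from the hospital/outpatient sector will be compiled for each cohort".
- **Payer (19.3).** Reimbursement by public and private payers is gathered from the participating institutions: "This information will come from data sources within each institution as compiled by an internal research assistant". The horizon is 1 to 3 years.
- **Patient (19.3).** Out-of-pocket care, work loss, worker replacement and lost productivity are listed. Unpaid family care time is not named.
- **Resource time (19.3, sampling of institutions).** Recorded contact includes contact "during the week with non-wound clinic staff (e.g., primary care physicians, home care nurse, RN etc", and the data feed average costs per group.
- **Worksheets (19.3).** Both arms' forms ask "How many nursing visits to patients home has patient received in the last 7 days to treat their ulcer", answered None, 1, 2, 3 or >3. Primary-care visits are No, or Yes with 1, 2, 3 or >3. Facility care is yes/no. The last item is free text: "Other non-clinic care? (please explain".
- **Return on investment (19.3 and 19.4).** It is taken from the hospital/outpatient perspective, over 6 to 12 treatment weeks, to show what the device is worth to the institution. Its costs include resource utilization, with no limit to clinic resources.

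**The concern.** A perspective determines whose costs count. Agency nurses, nursing-home staff and relatives are not on the wound clinic's budget, yet the only pricing rule for their time stands under the clinic's heading. The payer is the party likely to be billed for home nursing, outside primary care and facility care, and its costs are to come from institutions that need not hold those bills.

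Two results are exposed. The payer cost-effectiveness analysis is meant to show what faster healing saves over 1 to 3 years, but it has no stated source for care that an unhealed ulcer may need outside the clinic. The return on investment, offered to institutions as their own gain, may contain money that never passes through their accounts. Separately, a price per hour cannot be multiplied by a number of visits.

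**Working it through.** The plan states no cost figure to reproduce, and it gives no unit cost, outside-visit rate or expected cost difference. The check is therefore of the text, with the consequences in symbols.

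**1. Where each outside item is priced and who bears it**

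| Item | Priced under (19.3) | Borne by clinic? | Stated payer source? |
|---|---|---|---|
| Home nursing visits | Hospital/outpatient | No | None outside the institutions' own records |
| Outside primary care | Hospital/outpatient (general rule for care outside the clinic) | No | None outside the institutions' own records |
| Nursing-home staff | Hospital/outpatient | No | None outside the institutions' own records |
| Family caregiver | Hospital/outpatient | No | Not ordinarily a payer cost if unpaid |

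**2. Effect on the payer result.** Let D_p be the payer-reimbursed outside cost per patient, SOC minus CelluTome.

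- Full incremental payer cost (CelluTome minus SOC) = institutional increment − D_p.
- Payer cost as 19.3 describes it = institutional increment only.
- Error = as written − full = D_p.

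If D_p > 0, the plan overstates the graft's incremental cost to the payer. If D_p < 0, it understates it.

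**3. Effect on the return on investment.** Let D be the difference in all outside care, SOC minus CelluTome, valued by the hourly-wage rule. If outside care is counted in the hospital perspective, the clinic's net result moves by D: a credit if D > 0, a charge if D < 0. The route in is the non-clinic staff time collected in 19.3, together with unrestricted resource utilization in 19.4. Whether it is taken depends on how the closing sentence of the hospital paragraph is read:

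- If outside care is included, the clinic's return contains other parties' costs.
- If outside care is excluded, it is collected and priced but assigned to no perspective.

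Neither reading supplies the payer source missing in step 2.

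**4. Pricing rule against data**

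| Worksheet item | Recorded as | Needed for an hourly wage | Available? |
|---|---|---|---|
| Home nursing | None, 1, 2, 3, >3 | hours | No; the top category is also open-ended |
| Primary care | No, or Yes: 1, 2, 3, >3 | hours | No; the top category is also open-ended |
| Facility care | yes/no over 7 days | hours | No; not even days |
| Family care | free text only | hours | Only if volunteered |

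Cost = wage × hours, and the worksheets record minutes only for clinic staff.

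**The case against.** The best defence rests on two limits in the text. The sentence after the wage rule compiles costs from the hospital/outpatient sector, and 19.4 describes the return-on-investment benefits as averted complication costs that matter to the clinic. On that reading, an averted home visit never reaches the clinic's return. This stands to the extent that misattribution is permitted but not prescribed. It does not settle the matter: the benefit list is introduced as what benefits include, and the cost side of 19.4 carries no such limit.

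A second defence is that worksheet averages are computed per group without being tied to one perspective, and that 19.4 runs one model from all three viewpoints, so outside care could reach the payer result. It could, but the payer cost source that 19.3 actually names is institutional reimbursement, and nothing directs worksheet visits into it.

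Third, outside care is costed only as detected on the forms, the free-text line can capture family care, and a stated visit length would turn counts into hours. All true. But the plan states no visit length, and it would not resolve '>3' or the yes/no item.

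Finally, section 9.2 attaches no hypothesis to the economic outcomes. That limits how much the point matters, but the two outcomes are still named in section 3.

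**Conclusion.** The point holds in this form: 19.3 prices outside care only under a perspective that does not bear it, the payer result as written omits reimbursed outside care, the clinic's return on investment can include costs or savings belonging to others, and the hourly-wage rule cannot be applied to the data collected.

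Three stronger conclusions might be inferred, and the documents do not support them.

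- **That the clinic's return is credited with other parties' savings.** The text is ambiguous, and the sign depends on which arm uses more outside care.
- **That the clinic and payer results are wrong by the same amount in opposite directions.** D is over 6 to 12 weeks at wage rates and D_p over 1 to 3 years at reimbursement. Unpaid family care belongs in neither the clinic's nor, ordinarily, the payer's costs; the gap there is that the patient perspective does not name it.
- **That the effect can be sized in visits.** Section 9.3's healing assumptions could give time with an open ulcer, but no visit rate is stated, and 'None' is an allowed answer. Costing is also not done on the whole arm: 19.3 gives 5 worksheet patients per group per selected clinic and mentions eight clinics, so about 8 × 5 = 40 per group.

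No magnitude can be given. The healing and safety analyses are untouched. The verdict assumes that home agencies, outside physicians and nursing facilities bill separately from the participating clinics, which the documents do not state.

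**What to change.** In 19.3 and 19.4:

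1. Limit the hospital/outpatient perspective and the return on investment to costs the clinic bears: its own labour, supplies, drugs, diagnostics and CelluTome.
2. Carry home nursing, primary care and facility care from the worksheets into the payer perspective, at published payment rates instead of hourly wages.
3. Price the two count items per visit, with a stated value and a sensitivity range for '>3'.
4. For the yes/no facility item, state a weekly assumption with a sensitivity range. A per-day rate does not fit, because days are not recorded.
5. Put any family-caregiver time reported in the free-text line in the patient perspective.
6. State how in-trial outside-care use is extended over the 1 to 3 year payer horizon, since the worksheets cover only trial weeks.

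The cost is appendix wording, a set of published rates and a little more analysis work; no new data collection is needed. The downside is that the clinic's return on investment may look less favourable. If grafting does reduce outside care, the payer result would look better than under the present text.
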